## Secondary Outcome Measure: Measure Title CPAP Efficacy

Measure Description: Efficacy will be evaluated by measuring the apnea and hypopnea index (AHI) during treatment. The efficacy of standard CPAP and CPAP flex will be compared.

Statistical method:

Generalized estimating equations (GEE) models, with AHI as the dependent variable, will be used to compare the efficacy between standard CPAP and CPAP flex.

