2. Initially, the subject will be treated using the AutoCPAP program which varies the pressure, generally between 5 and 15 cm water, depending on the obstruction. If used regularly (for at least 4 hours a night for 2 nights), a fixed pressure will be automatically assigned. If the subject does not regularly use CPAP, treatment will continue using the autotitrate program. The technician will monitor CPAP treatment to ensure adequate treatment when the subject uses CPAP. The automated AHI is monitored to ensure efficacy of therapy (AHI of <10 events per hour of sleep). If the AHI is >10 events per hour of sleep the data is reviewed by a designated sleep physician and the pressure is modified or the patient is recommended for an in laboratory sleep study if indicated.

3. Adherence monitoring will be made from the CPAP machine for 1 month with first intervention, then switched to the alternate intervention and adherence monitored for another month. Data from last 2 weeks of each period will be used for objective adherence comparisons between interventions. Periods of reported non-use by the subject due to illness or travel will not be included in the treatment periods. The trial periods may be extended for up to 1 month due to instrument (CPAP machine or modem) failure. Instrument failure is not expected to exceed 10% of the users. At the end of the trial, subjects will be asked to return the modem either by mail or in person. If the subject returns the modem in person, he/she will be asked to repeat the nasal lavage sample. The subject will be informed that the purpose of this sample is to collect preliminary data. The pre-CPAP and post-CPAP samples will be compared to determine if CPAP use has any effect on markers in the lavage sample.

4. Subjective assessment of sleepiness, quality of life and satisfaction with therapy will be obtained using questionnaires administered at the start and end of each period.

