Randomization and Blinding: OSA patients will be randomly allocated to CPAP or CPAPFlex stratified by site and low ( $\log[\text{Reff}] \leq 1.0$ ) and high ( $\log[\text{Reff}] > 1.0$ ) resistance by the statistician. This will be accomplished by generating an allocation table of randomly permuted blocks of assignments to study condition (CPAP vs CPAPFlex) for each site. Outcome of the randomized choice of treatment will be provided to an unblinded individual (one at each site) who is not part of the analysis of the study data, and who will set the allocated CPAP device at the start of each treatment period. Devices will be tracked by serial number. Although subjects will be blinded to the therapy type, they may be able to perceive a difference in the mask pressure during expiration. CPAP and CPAPFlex machines are identical otherwise and no feedback will be provided to subjects regarding the type of treatment. The unblinded individual (not the PI) will maintain a master file containing numbered sealed envelopes containing the serial number, patient ID and designation code for each treatment period and subject. Except in an emergency situation these envelopes will not be opened until the study has been completed and all data have been entered/cleaned. The unblinded individual will document any premature unblinding that may occur. All data review relevant to adherence/titration scoring will be presented to the scorer as a flow signal alone, keeping the pressure data unvisualized so as not to reveal the presence of CPAPFlex. The automated report will indicate if there are significant deviations from prescribed pressure.

Monitoring of CPAP Efficacy and Adherence: Efficacy will be evaluated by (i) reviewing residual AHI and inspiratory flow limitation at optimal pressure as recorded on the device and (ii) review of raw airflow signal. Nightly adherence at the optimal pressure is recorded on the device and also transmitted to the sleep center.

Cross over to alternate therapy: Four weeks after the first intervention (ie CPAP or CPAPFlex), the device will be switched to the alternate mode by remote modem connection. The switch will take place after the subject has completed the telephone satisfaction questionnaire.

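### Does adjusting pressure when AHI exceeds 10 make the SAP's AHI comparison of CPAP and CPAPFlex uninterpretable?

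*SAP*

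**What the plan says.** The SAP, under its secondary outcome (CPAP Efficacy), states: "Efficacy will be evaluated by measuring the apnea and hypopnea index (AHI) during treatment". The method is one sentence: "Generalized estimating equations (GEE) models, with AHI as the dependent variable, will be used to compare the efficacy between standard CPAP and CPAP flex". It gives no time window, no pressure state and no count of pressure changes.

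Protocol section 3, Protocol for SA3, item 2, sets a target AHI below 10 on treatment. Above 10, a sleep physician reviews the data "and the pressure is modified or the patient is recommended for an in laboratory sleep study if indicated". Subjects who do not use the device regularly stay on autotitration. Item 3 fixes a window for adherence only: "Data from last 2 weeks of each period will be used for objective adherence comparisons between interventions".

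In Procedures for SA3, the paragraph on monitoring efficacy and adherence says efficacy is assessed by "reviewing residual AHI and inspiratory flow limitation at optimal pressure as recorded on the device", together with the raw airflow signal. At cross-over, "the device will be switched to the alternate mode by remote modem connection". The visible text does not say whether a pressure changed in period 1 carries into period 2.

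**The concern.** The same AHI that triggers a correction is later the outcome. If CPAPFlex controlled events less well, more of its users would exceed 10, more would have their pressure changed, and the recorded AHI would move back towards that of standard CPAP. The SAP names no outcome for corrections, in-laboratory referrals or delivered pressure by mode, so nothing in it would show that one mode needed more help to reach the same AHI.

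Protocol section 6 already asserts that the two modes are equally effective, so a null result could be taken as confirmation. At stake is the reading of one secondary endpoint. The adherence comparison is not touched.

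**Working it through.** There is no stated figure to reproduce: the visible text gives no AHI standard deviation, effect size, margin or rate of AHI above 10. The calculation below is illustrative.

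**Inputs.** From the protocol (Protocol for SA3, items 1 and 2): about 500 subjects with OSA, about 10% refusing CPAP, so 500 × 0.9 = 450; trigger at AHI 10. Assumed: log-normal AHI with median m and log-SD s; a corrected value is Uniform(3,10), mean 6.5; within-subject correlation 0.6 on the log scale; two-sided 5% paired t-test standing in for a two-period GEE; pressure reset between periods.

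**Loss of mean difference.** With k = (ln 10 − ln m)/s:
- mean before correction: M = m·exp(s²/2)
- share above 10: p = 1 − Φ(k)
- part of the mean above 10: U = M·[1 − Φ(k − s)]
- mean if all above 10 are corrected: M − U + 6.5p

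For medians 4 v 5, s = 0.8:
- m = 4: M = 5.51, p = 0.126, U = 2.01; after correction 5.51 − 2.01 + 0.82 = 4.32.
- m = 5: M = 6.89, p = 0.193, U = 3.26; after correction 6.89 − 3.26 + 1.26 = 4.88 (from unrounded values).
- The difference falls from 1.38 to 0.56 events/h, so 59% is lost.

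**Effect on the test.** Correction also removes the long upper tail. In simulation the SD of the paired difference falls from about 5.81 to 2.59. The standard error falls from 5.81/√450 = 0.274 to 2.59/√450 = 0.122. The ratio of difference to standard error goes from 1.38/0.274 = 5.0 to 0.56/0.122 = 4.6. More than half the difference disappears, yet the evidence against equality barely weakens.

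| Medians, log-SD | Above 10 | Difference, none → all corrected | Lost | Power: none / half / all corrected |
|---|---|---|---|---|
| 2 v 2.5, 0.6 | 0.4% v 1.0% | 0.60 → 0.56 | 7% | at least 99% throughout |
| 2 v 2.5, 0.8 | 2.2% v 4.2% | 0.69 → 0.52 | 24% | at least 99% throughout |
| 3 v 3.75, 0.8 | 6.6% v 11.0% | 1.03 → 0.58 | 44% | about 100 / 99 / 100% |
| 4 v 5, 0.8 | 12.6% v 19.3% | 1.38 → 0.56 | 59% | about 100 / 97 / 99% |
| 5 v 6.25, 0.8 | 19.3% v 27.8% | 1.72 → 0.51 | 70% | about 100 / 95 / 98% |
| 4 v 6, 0.8 | 12.6% v 26.2% | 2.75 → 0.98 | 64% | 100% throughout |

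**Would counting corrections do better?** In these cases it does not. A McNemar comparison of the share above 10 (no continuity correction) has about 25% power in the first row, 94% for 4 v 5 and 97% for 5 v 6.25, in each case no better than the AHI test.

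**Smaller samples.** For 4 v 5 with 225 subjects, power with none, half or all corrected is about 93–96%, 84–85% and 88–91% across runs. With 100 subjects it is about 70%, 50% and 57%. At that size the test is weak even without corrections.

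**Where masking is real.** With median 4.5, log-SD 0.7 and N = 450, suppose 10% of patients have 8 extra events/h on CPAPFlex. The difference of 0.80 falls to 0.42, 0.20 or 0.07 when 50%, 80% or 100% of corrections succeed. Power falls from about 93% to 51%, 22% or 10%. Correction rates of about 12.7% v 20% would be told apart with about 94–95% power. A uniform 10% worsening also loses power, from about 75% to between 49% and 36%, but there the count has only about 37%, so it adds nothing.

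**Pressure kept at cross-over.** For 4 v 5 with all corrected, keeping the period 1 pressure gives a mode difference of 0.68 and a period effect of −0.34 events/h. The mode difference is not wiped out. Order is randomised in permuted blocks, so a period shift falls about equally on both modes.

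**The case for a change.** The strongest case for acting is that the steering is real, the SAP does not acknowledge it, and its wording on treatment AHI could cover nights before a correction, after it, or both. Even with AHI at titrated pressure as the stated target, AHI alone cannot show that one mode needed more adjustment. In the subgroup scenario the AHI test nearly fails while a count of corrections succeeds. A dated log of changes would be hard to rebuild later.

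Most of this stands as description. It does not show that the planned analysis gives a wrong answer. The subgroup scenario is an assumption with no support in the documents. A non-significant difference test with no margin cannot establish equal efficacy, with or without corrections, and the SAP does not claim that it would. A count would also miss subjects left on autotitration, whose pressure adjusts with no physician decision to record. Using AHI before any change as the outcome brings its own difficulty: if the period 1 pressure is kept, that measure carries a period effect of about −1.05 events/h for 4 v 5.

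The statement that corrections are not compared by mode holds only for the visible text. Protocol section 3 has redacted blocks, and the numbering runs from section 4 to section 6 across further redacted text.

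**Conclusion.** No change follows. Pressure adjustment is part of how each mode is delivered, and the protocol's description of efficacy at optimal pressure points to AHI after adjustment. Comparing that quantity by GEE is a sound comparison of the two modes as used. Analysts would ordinarily take the window from the adherence rule and fit a period term in a two-period crossover. Leaving these unwritten is a gap in detail that does not bias the mode comparison.

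The attenuation is real, at 7% to 70% of the mean difference when CPAPFlex AHI is 25% higher and every value above 10 is corrected. With about 450 subjects, power still stays at about 95% or more. This rests on log-normal AHI, correlation 0.6, a paired t-test in place of GEE, and no loss beyond the 10% refusal. It would not hold with far fewer completers, for a small uniform worsening, or for an excess confined to patients pushed above the trigger. A correction count would clearly add information only in the last of these. It is a reasonable descriptive extra for a secondary endpoint, and the planned result does not depend on it.
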